7.1 Investigational Agent

Nivolumab is a human monoclonal antibody that blocks the interaction between PD-1 and its ligands, PD-L1 and PD-L2. Nivolumab is an IgG4 kappa immunoglobulin that has a calculated molecular mass of 146 kDa. Binding of the PD-1 ligands, PD-L1 and PD-L2, to the PD-1 receptor found on T cells, inhibits T-cell proliferation and cytokine production. Upregulation of PD-1 ligands occurs in some tumors and signaling through this pathway can contribute to inhibition of active T-cell immune surveillance of tumors. Nivolumab is a human immunoglobulin G4 (IgG4) monoclonal antibody that binds to the PD-1 receptor and blocks its interaction with PD-L1 and PD-L2, releasing PD-1 pathway-mediated inhibition of the immune response, including the anti-tumor immune response. In syngeneic mouse tumor models, blocking PD-1 activity resulted in decreased tumor growth.

7.2 Availability

Nivolumab is an investigational agent supplied to investigators by Bristol-Myers Squib

7.3 Preparation and Administration of Nivolumab

Dose Calculations

For Multiple myeloma: Nivolumab is given every 2 weeks. The recommended dose of nivolumab is a flat dose of 240mg administered as an intravenous infusion over 30 minutes every 2 weeks until disease progression or unacceptable toxicity.

Visually inspect drug product solution for particulate matter and discoloration prior to administration. Nivolumab is a clear to opalescent, colorless to pale-yellow solution. Discard the vial if the solution is cloudy, discolored, or contains extraneous particulate matter other than a few translucent-to-white, proteinaceous particles. Do not shake the vial.

7.4 Dose Modifications, Delays or Discontinuation of Nivolumab

Recommendations for OPDIVO modifications are provided in Table 1. There are no recommended dose modifications for hypothyroidism or hyperthyroidism. Interrupt or slow the rate of infusion in patients with mild or moderate infusion reactions. Discontinue OPDIVO in patients with severe or life-threatening infusion reactions.

Table 1: Recommended Dose Modifications for OPDIVO

Adverse Reaction	Severity*	Dose Modification
Colitis	Grade 2 diarrhea or colitis	Withhold dose ^a
	Grade 3 diarrhea or colitis	Withhold dose ^a when administered as a single agent
	Grade 4 diarrhea or colitis	Permanently discontinue when administered with ipilimumab
Pneumonitis	Grade 2 pneumonitis	Withhold dose ^a
	Grade 3 or 4 pneumonitis	Permanently discontinue
Hepatitis/non-HCC ^b	Aspartate aminotransferase (AST) or alanine aminotransferase (ALT) more than 3 and up to 5 times the upper limit of normal (ULN) or total bilirubin more than 1.5 and up to 3 times the ULN	Withhold dose ^a
	AST or ALT more than 5 times the ULN or total bilirubin more than 3 times the ULN	Permanently discontinue
Hepatitis/ HCC ^b	
 If AST/ALT is within normal limits at baseline and increases to more than 3 and up to 5 times the ULN If AST/ALT is more than 1 and up to 3 times ULN at baseline and increases to more than 5 and up to 10 times the ULN If AST/ALT is more than 3 and up to 5 times ULN at baseline and increases to more than 8 and up to 10 times the ULN 	Withhold dose ^a

Table 1: Recommended Dose Modifications for OPDIVO

Adverse Reaction	Severity*	Dose Modification
	If AST or ALT increases to more than 10 times the ULN or total bilirubin increases to more than 3 times the ULN	Permanently discontinue
Hypophysitis	Grade 2 or 3 hypophysitis	Withhold dose ^a
	Grade 4 hypophysitis	Permanently discontinue
Adrenal Insufficiency	Grade 2 adrenal insufficiency	Withhold dose ^a
	Grade 3 or 4 adrenal insufficiency	Permanently discontinue
Type 1 Diabetes Mellitus	Grade 3 hyperglycemia	Withhold dose ^a
	Grade 4 hyperglycemia	Permanently discontinue
Nephritis and Renal Dysfunction	Serum creatinine more than 1.5 and up to 6 times the ULN	Withhold dose ^a
	Serum creatinine more than 6 times the ULN	Permanently discontinue
Skin	Grade 3 rash or suspected Stevens-Johnson syndrome (SJS) or toxic epidermal necrolysis (TEN)	Withhold dose ^a
	Grade 4 rash or confirmed SJS or TEN	Permanently discontinue
Encephalitis	New-onset moderate or severe neurologic signs or symptoms	Withhold dose ^a
	Immune-mediated encephalitis	Permanently discontinue
Other	Other Grade 3 adverse reaction First occurrence Recurrence of same Grade 3 adverse reactions	Withhold dose ^a Permanently discontinue
	Life-threatening or Grade 4 adverse reaction	Permanently discontinue
	Grade 3 myocarditis	Permanently discontinue
	Requirement for 10 mg per day or greater prednisone or equivalent for more than 12 weeks	Permanently discontinue
	Persistent Grade 2 or 3 adverse reactions lasting 12 weeks or longer	Permanently discontinue

* Toxicity was graded per National Cancer Institute Common Terminology Criteria for Adverse Events, Version 4.0 (NCI CTCAE v4).

^a Resume treatment when adverse reaction improves to Grade 0 or 1.

^b HCC: hepatocellular carcinoma.

^c Resume treatment when AST/ALT returns to baseline.

8 Correlative Studies

8.1 Bone Marrow tissue aspirate

In addition to this, 20 ml sample of bone marrow tissue will be collected at the same intervals.

8.2 Tissue biopsies

4 core pre treatment tissue biopsies will be taken for diagnostic confirmation and correlative studies.

8.3 Other studies :

A baseline sputum (saliva) sample will be obtained from all patients for gene expression profiles.

8.4 Microbiome samples

Stool collection for microbiome analysis will be collected at Baseline, end of radiation, C4D1 and C7D1. to explore changes of the microbiome during ICB. Appendix 2 describes the protocol for stool collection.

9 Measurement of Effect

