2.6 Microbiome Correlative studies

2.6.1 To explore associations of ORR with changes in the microbiome.

While immune checkpoint blockade results in remarkably prolonged disease control in a subset of patients^{47,48} modulators of this phenotype are not well understood. Accumulating evidence suggests the gut microbiota play a critical role in response to both anti-PD-L1 efficacy and CTLA-4 blockade: two recently published studies by Vetizou *et al.* and Sivan *et al.* demonstrated in mouse models that the gut microbiome critically impacts response to immunotherapy^{47,48}. Remarkably, by altering the composition of commensal microbiota, the response to CTLA-4 blockade and anti-PD-L1 therapy could be manipulated and therapeutic response markedly enhanced. These pre-clinical studies provide strong rationale for our hypothesis that the human gut microbiome composition will

correlate with response to ICB and RT. Identification of commensal organisms harbored in patients with heightened antitumor immune response can ultimately be manipulated to achieve desired outcomes in a greater proportion of patients. Fecal transplant is an established clinical technique whereby microbiota can be transferred into humans to induce select therapeutic outcomes, providing direct clinical applicability of any findings ⁴⁹.

The study by Vetizou *et al.* underscores the dependence of CTLA-4 blockade on commensal microbiota ⁴⁸. First, the authors demonstrate that anti-CTLA-4 therapy is ineffective in mice that are housed in germ-free cages or treated with antibiotics.

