Taken together, the above preclinical studies lend strong support towards collection of gut microbiome samples from patients enrolling on all future immunotherapy studies. We propose to collect stool samples from study patients before treatment and at day 21, 3 months and 6 months for analysis of microbiome composition and changes after ICB and RT. Both pre-clinical and clinical data demonstrate that the addition of RT to ICB creates a robust immune response, eliciting anti-tumor immune responses in otherwise non-responding patients. Given that we expect a similar heightened response in our proposed study, our patient cohort with its expected dichotomous outcomes will be particularly suitable for microbiome analysis. The results will be an important step towards understanding, and ultimately harnessing, the interplay between the human gut microbiome and anti-tumor immune response.

Methods Stool collection will occur before treatment, at day 21, at 3 months and 6 months to

explore changes of the microbiome during ICB. Bacterial diversity and taxonomy will be estimated by high throughput sequencing (HTS) of 16S rRNA amplicons, using the MiSeq platform in the Genomic Technology Core Lab. Methods have been established in the Blaser Lab and proven to yield accurate and reproducible results.^{50,51} Analysis will be based on the QIIME (Quantitative Insights into Microbial Ecology) software package developed by the Knight lab,⁵² and machine learning analyses developed by NYU Center for Health informatics and Bioinformatics (CHIBI) investigators working on NYU Human Microbiome Program studies.^{53,54} Appendix 2 describes the protocol for stool collection.

3 Subject Selection

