5.1 Schedule of Assessment

Procedure	Screening (Day 0)	C1D1 (±3 days)	C1D15 (±3 days)	Cycles 2-4		Cycles 5+	Cycles 5+	End of Study
				D1	D15	D1	D15	
Informed Consent	X							
Medical History	X	X		X		X	X	X
Physical Exam	X	X		X		X	X	X
Vital Signs + weight	X	X	X	X	X	X	X	X
Performance Status (ECOG)	X	X		X		X	X	X
Concomitant Medications	X	X	X	X	X	X	X	X
Second Primary Malignancy	X	X	X	X	X	X	X	X
Adverse Events Assessment	X	X	X	X	X	X	X	X
Bone Marrow Aspiration/Biopsy ^a	X ^a			X ^a		X ^a		X ^a
Biopsy of Targeted Lesion	X							
Radiologic bone imaging:								
PET/CT, MRI	X				X			X
CBC w/ plts & diff	X	X	X	X	X	X	X	X
CMP, Mg, Uric Acid, LDH	X	X	X	X	X	X	X	X
Serum or urine pregnancy test	X	X	X	X	X	X	X	X
TSH	X			X		X		
Beta 2 microglobulin	X			X				
Response Assessment								
Serum quantitative immunoglobulins	X	X		X		X		X
free light chains, SPEP & SIFE	X	X		X		X		X
24-Hour urine for urine total protein	X	X		X		X		X
UPEP & UIFE	X	X		X		X		X
TREATMENT								
Nivolumab Infusion ^c		X ^c	X ^c	X ^c	X ^c	X ^c	X ^c	
Radiation to Targeted Lesion ^b		X ^b						
RESEARCH PROCEDURES								
Stool Samples (before nivo infusion) ^d		X ^d			X ^d	X ^d		
Saliva Sample collection (before nivo)		X						

Foot notes:

- a. Bone marrow aspirate pre-nivolumab infusion on C2D1, C4D1, C7D1, C10D1 and Q 12 weeks thereafter and as needed to confirm CR
- b. One course of radiation (6GY x 5 fractions), with first radiation on D1 AFTER IV nivolumab
- c. All Infusions will have a ± 3 day window.
- d. Stool samples will be collected on Day1, end of Radiation, C4D1 and C7D1.

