5.1.2 Treatment Phase

Once eligible, patients will receive immunotherapy, nivolumab, intravenously at 240 mg every two weeks. Infusions will be given over 30 minutes (not bolus or IV push). Patients will also receive radiation of 6 Gy x 5 fractions the first week of starting immunotherapy. Immunotherapy treatment starts with the first radiotherapy fraction. Nivolumab will be given every 2 weeks. Patients will have specified laboratory values measured monthly and evaluated for response as defined by International Myeloma Working Group Criteria. Patients will continue to receive their respective immunotherapy for up to three years or until disease progression or dose limiting toxicity is reached. Patients will remain on therapy for up to 6 cycles in the setting of stable disease and for up to a year in the setting of a PR or better by 6 cycles.

5.2 Response Assessment at Week 12

Patients will have specified laboratory values measured monthly and evaluated for response as defined by International Myeloma Working Group Criteria. Patients without progression of disease as defined by IMWG criteria including assessment of plasmacytoma(s) by PET/CT will continue to receive nivolumab every 2 weeks.

5.3 Duration of Therapy and Criteria for Removal from Study:

In the absence of treatment delays due to adverse event(s), treatment may continue until one of the following criteria applies:

1. Progression of disease as defined by IMWG criteria,
2. Intercurrent illness that prevents further administration of treatment,
3. Unacceptable adverse event(s),
4. Patient decides to withdraw from the study, or
5. General or specific changes in the patient's condition render the patient unacceptable for further treatment in the judgment of the investigator.

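### C4D1 and C7D1 stool is collected only from patients still on nivolumab, so whether a late microbiome sample exists depends on outcome

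*Combined protocol and SAP*

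**What the plan says.** Section 8.4 gives four stool time points: "Stool collection for microbiome analysis will be collected at Baseline, end of radiation, C4D1 and C7D1". Footnote d of the calendar in 5.1 repeats them ("Stool samples will be collected on Day1, end of Radiation, C4D1 and C7D1"), as does Appendix 2. The calendar row is labelled "Stool Samples (before nivo infusion", which ties C4D1 and C7D1 stool to infusion visits. No stool is listed at end of study or after treatment stops.

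Section 2.6 still has a different schedule: "Stool collection will occur before treatment, at day 21, at 3 months and 6 months". Its aim is headed "To explore associations of ORR with changes in the microbiome".

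On treatment duration, the last sentence of 5.1.2 makes the limit depend on response: "for up to 6 cycles in the setting of stable disease and for up to a year in the setting of a PR or better", where that response must be reached within six cycles. The sentence before it allows up to three years, or until progression or dose-limiting toxicity. Section 5.2 continues every patient without progression, 5.3 lists no stop for stable disease, and the synopsis and 7.3 treat until progression or toxicity.

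Section 11.5 tests alpha diversity against time relative to radiation by one-way ANOVA. It also plans a paired signed-rank test of relative abundance and linear mixed models over time. It does not mention samples missing because of outcome.

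**The concern.** The aim relates response to change in the microbiome, and 2.6 counts on the cohort dividing into two outcome groups. A sample that exists only while treatment continues is itself selected on outcome.

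Two things follow. First, the late contrast loses patients mainly from the non-responding side. Second, an analysis over time that does not match samples within patient compares everyone at baseline with a selected subset later. If patients who stay on treatment already differed at baseline, that difference appears as a change over time even when no patient's microbiome has changed.

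**Working it through.** The plan gives no sample size or power for the microbiome aim, so there is no stated figure to reproduce. The check sets the visit days against the duration rules and then sizes the result.

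**1. Visit days.** Infusions fall on D1 and D15 at two-week intervals. The marrow schedule runs C4D1, "C7D1, C10D1 and Q 12 weeks thereafter", so three cycles take 12 weeks and one cycle is 28 days (inferred). Day of D1 in cycle c = (c − 1) × 28 + 1.
- C4D1: 3 × 28 + 1 = day 85. That is 84 days (12 weeks, about 2.8 months) after first dose.
- C7D1: 6 × 28 + 1 = day 169. That is 168 days (24 weeks, about 5.5 months) after first dose.
- Last infusion within six cycles, C6D15: 5 × 28 + 15 = day 155, which is before C7D1.

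C4D1 and C7D1 are thus the nearest visits to the 3 and 6 months of 2.6. The second time point also differs between the sections: 2.6 says day 21, whereas 8.4 says end of radiation, which 5.1.2 places in the first week.

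**2. Who has a C7D1 infusion visit.**
- Last sentence of 5.1.2: patients with PR or better by cycle 6. Stable disease ends at day 155 or earlier. Minimal response, a separate category in 9.1, falls under neither branch.
- Preceding sentence of 5.1.2, 5.2, 5.3, 7.3 and the synopsis: all patients free of progression and not stopped for toxicity or another reason, including stable disease and minimal response.
- Either reading: patients who have progressed are off treatment and have no scheduled C7D1 stool. C4D1 likewise loses those who progress before week 12.

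**3. Number sampled if the six-cycle limit applies.** Assume that the rate of PR or better by cycle 6 lies between the two design rates in 11.1 (20% and 40%), and ignore dropout.
- 26 × 0.20 = 5.2 and 26 × 0.40 = 10.4, so about 5 to 10 patients give C7D1 stool.
- 26 − 5.2 = 20.8 and 26 − 10.4 = 15.6, so about 16 to 21 do not.

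This multiplication should not be carried over to a trial stopped after 13 patients, because stopping requires three or fewer responses.

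**4. Apparent time effect in an unmatched analysis, same reading.** Let p be the rate of PR or better and D the baseline difference in a diversity index between those patients and the rest. Suppose that nobody changes.
- Baseline mean of all patients = mean of the rest + p × D.
- C7D1 mean = mean of the rest + D.
- Apparent change = (1 − p) × D, which is 0.8 D at p = 0.20 and 0.6 D at p = 0.40.

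The documents give no value for D. With D = 0.5 SD, purely as an illustration, the shift would be 0.40 to 0.30 SD; with D = 0 there is none. If treatment runs to progression, the multiplier is instead the proportion off treatment by C7D1, which the documents do not give.

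**The case against.** A reader might infer that nobody with stable disease or progression can be compared at C7D1, so that one side of the contrast is empty by design. The documents do not support that. It takes the six-cycle sentence as settled, while the preceding sentence, 5.2, 5.3, 7.3 and the synopsis set no response condition, and the calendar has an unrestricted column for cycles 5 onward. In addition, response is classified at week 12 (section 11). Even under the six-cycle limit, a week-12 non-responder who reaches PR by cycle 6 still gives C7D1 stool. The response contrast also remains available at baseline, end of radiation and, with some loss, C4D1.

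Three further points favour the plan:
- Section 8.4 says that stool is for studying change during checkpoint blockade, so on-treatment sampling may be intended.
- Section 11.5 names no comparison of response groups at C7D1.
- The paired test is protected against baseline differences between patients, and the mixed model is much less exposed than the ANOVA. Section 11.5 says that the mixed model will also be fitted to the ecological indices.

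These points narrow the concern but do not remove it. Progressors are missing at C7D1 under every reading, the aim in 2.6 is association with response, and no within-patient method can supply a group that was never sampled. The unmatched ANOVA stays in the plan beside the mixed model, with nothing said about which governs.

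**Conclusion.** The concern holds in a limited form. Late stool is conditional on still receiving treatment, which excludes progressors in all cases and stable-disease patients if the six-cycle sentence applies. The late responder contrast is depleted, not necessarily empty, and the one-way ANOVA on time can read selection as change.

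The figure of about 5 to 10 of 26 patients at C7D1 rests on the six-cycle limit applying, a 20-40% rate of PR or better by cycle 6, and no dropout. If treatment runs to progression, more patients are sampled and that figure does not apply; the selection is smaller but remains. The size of any spurious time effect depends on a baseline difference that the documents do not give.

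The aim is exploratory (listed in the synopsis, not in 1.3), so the consequence is confined to the microbiome results.

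**What to change.** 1. Reconcile the duration passages (both sentences of 5.1.2, 5.2, 5.3, 7.3 and the synopsis), including the status of minimal response. This point takes no position on which rule is right.
2. In 8.4, footnote d of 5.1 and Appendix 2, tie the last two stool samples to calendar time, about weeks 12 and 24 from first dose, whether or not nivolumab continues. This agrees with the 3 and 6 months in 2.6; align the rest of 2.6, including its day 21 sample, with 8.4. Use the existing home kit; 5.4 already follows patients for three years after removal. Flag samples taken off treatment or after new therapy.
3. In any case, replace the one-way ANOVA on time in 11.5 with the mixed model already specified there for the indices, and report C7D1 results as describing patients still on treatment.

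The cost is protocol wording and a few extra home kits. The downside is that some late samples will be affected by later therapy, which is why they need a flag. The change to the analysis costs nothing.

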9.1 Standard IMWG Response Criteria

Response to multiple myeloma will be assessed based on the International Myeloma Working Group Criteria (IMWG) as described in the table below.

Standard IMWG response criteria*	
Stringent complete response	Complete response as defined below plus normal FLC ratio** and absence of clonal cells in bone marrow biopsy by immunohistochemistry (κ/λ ratio $\leq 4:1$ or $\geq 1:2$ for κ and λ patients, respectively, after counting ≥ 100 plasma cells)++
Complete response	Negative immunofixation on the serum and urine and disappearance of any soft tissue plasmacytomas and $< 5\%$ plasma cells in bone marrow aspirates
Very good partial response	Serum and urine M-protein detectable by immunofixation but not on electrophoresis or $\geq 90\%$ reduction in serum M-protein plus urine M-protein level $< 100\text{mg per 24 hours}$.
Partial response	$\geq 50\%$ reduction of serum M-protein plus reduction in 24 h urinary M-protein by $\geq 90\%$ or to $< 200\text{ mg per 24h}$; If the serum and urine M-protein are unmeasurable, a $\geq 50\%$ decrease in the difference between involved and unininvolved FLC levels is required in place of the M-protein criteria; If serum and urine M-protein are unmeasurable, and serum-free light assay is also unmeasurable, $\geq 50\%$ reduction in plasma cells is required in place of M-protein, provided baseline bone marrow plasma-cell percentage was $\geq 30\%$. In addition to these criteria, if present at baseline, a $\geq 50\%$ reduction in the size (SPD)§§ of soft tissue plasmacytomas is also required.
Minimal response	$\geq 25\%$ but $\leq 49\%$ reduction of serum M-protein and reduction in 24-h urine M-protein by 50–89%. In addition to the above listed criteria, if present at baseline, a $\geq 50\%$ reduction in the size (SPD)§§ of soft tissue plasmacytomas is also required.

Stable disease	Not recommended for use as an indicator of response; stability of disease is best described by providing the time-to-progression estimates. Not meeting criteria for complete response, very good partial response, partial response, minimal response, or progressive disease
Progressive disease ^{††,Ω}	
Any one or more of the following criteria:
 
Increase of 25% from lowest confirmed response value in one or more of the following criteria:
 
 Serum M-protein (absolute increase must be ≥ 0.5 g/dL); Serum M-protein increase ≥ 1 g/dL, if the lowest M component was ≥ 5 g/dL; Urine M-protein (absolute increase must be ≥ 200 mg/24 h); 
In patients without measurable serum and urine M-protein levels, the difference between involved and uninvolved FLC levels (absolute increase must be > 10 mg/dL);
 
In patients without measurable serum and urine M-protein levels and without measurable involved FLC levels, bone marrow plasma-cell percentage irrespective of baseline status (absolute increase must be $\geq 10\%$); Appearance of a new lesion(s), $\geq 50\%$ increase from nadir in SPD^{§§} of > 1 lesion, or $\geq 50\%$ increase in the longest diameter of a previous lesion > 1 cm in short axis;
 
$\geq 50\%$ increase in circulating plasma cells (minimum of 200 cells per μL) if this is the only measure of disease

Clinical relapse	
Clinical relapse requires one or more of the following criteria: Direct indicators of increasing disease and/or end organ dysfunction (CRAB features) related to the underlying clonal plasma-cell proliferative disorder. It is not used in calculation of time to progression or progression-free survival but is listed as something that can be reported optionally or for use in clinical practice; Development of new soft tissue plasmacytomas or bone lesions (osteoporotic fractures do not constitute progression);
 
Definite increase in the size of existing plasmacytomas or bone lesions. A definite increase is defined as a 50% (and ≥ 1 cm) increase as measured serially by the SPD^{§§} of the measurable lesion;
 
Hypercalcaemia (> 11 mg/dL);
 
Decrease in haemoglobin of ≥ 2 g/dL not related to therapy or other non-myeloma-related conditions; Rise in serum creatinine by 2 mg/dL or more from the start of the therapy and attributable to myeloma;
 
Hyperviscosity related to serum paraprotein

Relapse from complete response (to be used only if the end point is disease-free survival)	
Any one or more of the following criteria:
 
Loss of MRD negative state (evidence of clonal plasma cells on NGF or NGS, or positive imaging study for recurrence of myeloma);
 
Reappearance of serum or urine M-protein by immunofixation or electrophoresis;
 
Development of $\geq 5\%$ plasma cells in the bone marrow;
 
Appearance of any other sign of progression (ie, new plasmacytoma, lytic bone lesion, or hypercalcaemia)

*Derived from international uniform response criteria for multiple myeloma. Minor response definition and clarifications derived from Rajkumar and colleagues. When the only method to measure disease is by serum FLC levels: complete response can be defined as a normal FLC ratio of 0·26 to 1·65 in addition to the complete response criteria listed previously. Very good partial response in such patients requires a $\geq 90\%$ decrease in the difference between involved and unininvolved FLC levels. All response categories require two consecutive assessments made at any time before the institution of any new therapy; all categories also require no known evidence of progressive or new bone lesions or extramedullary plasmacytomas if radiographic studies were performed. Radiographic studies are not required to satisfy these response requirements. Bone marrow assessments do not need to be confirmed. Each category, except for stable disease, will be considered unconfirmed until the confirmatory test is performed. The date of the initial test is considered as the date of response for evaluation of time dependent outcomes such as duration of response.
	

**All recommendations regarding clinical uses relating to serum FLC levels or FLC ratio are based on results obtained with the validated Freelite test (Binding Site, Birmingham, UK).
	

++Presence/absence of clonal cells on immunohistochemistry is based upon the $\kappa/\lambda/L$ ratio. An abnormal κ/λ ratio by immunohistochemistry requires a minimum of 100 plasma cells for analysis. An abnormal ratio reflecting presence of an abnormal clone is κ/λ of $>4:1$ or $<1:2$. §§Special attention should be given to the emergence of a different monoclonal protein following treatment, especially in the setting of patients having achieved a conventional complete response, often related to oligoclonal reconstitution of the immune system. These bands typically disappear over time and in some studies have been associated with a better outcome. Also, appearance of monoclonal IgG κ in patients receiving monoclonal antibodies should be differentiated from the therapeutic antibody.
	

§§Plasmacytoma measurements should be taken from the CT portion of the PET/CT, or MRI scans, or dedicated CT scans where applicable. For patients with only skin involvement, skin lesions should be measured with a ruler. Measurement of tumor size will be determined by the SPD.
	

##Positive immunofixation alone in a patient previously classified as achieving a complete response will not be considered progression. For purposes of calculating time to progression and progression-free survival, patients who have achieved a complete response and are MRD-negative should be evaluated using criteria listed for progressive disease. Criteria for relapse from a complete response or relapse from MRD should be used only when calculating disease-free survival.
	

Ω In the case where a value is felt to be a spurious result per physician discretion (eg, a possible laboratory error), that value will not be considered when determining the lowest value.
	

10 Data Reporting / Regulatory Considerations

